
	
All remaining Group 2 subjects will enter Cohort 3 in ARC004 EM and will be randomized in a 1:1:1 ratio to ongoing treatment with AR101.
 
• Cohort 3A: QD for 56 weeks• Cohort 3B: QD for 28 weeks followed by QOD for 4 weeks and then BIW for 24 weeks, as tolerated• Cohort 3C: QD for 28 weeks followed by QOD for 4 weeks and BIW for 24 weeks, and finally QW for 28 weeks, as tolerated. 
At the end of each treatment period, qualifying subjects will undergo a maximum 4043 mg cumulative Exit DBPCFC and complete participation in ARC004.
 
The Exit Visit will complete subject participation in ARC004 with one exception: If a study site has not yet received approval for ARC008, subjects will receive additional AR101 and will continue dosing and visits in ARC004 until ARC008 is able to accept these subjects at the study site. Subjects will return to the study site for an unscheduled visit every 14 weeks to receive AR101 sachets for dosing at home and to ensure subject safety.
 
Throughout ARC004 EM, the first 2 doses at extended dosing intervals (BIW, QW, and QOW) will be administered under direct supervision in the clinic; QOD doses may be initiated at home. Thereafter, the doses will be administered at home as tolerated, and recorded in the subject diary. Investigators may, at their discretion, bring subjects back to the research unit for an observed dose at any time. All AR101 doses will be judged by the investigator to be tolerated or not tolerated according to criteria previously established in ARC003 and specified in Section 6.5.2.
 
Any subject receiving nondaily dosing (QOD, BIW, QW, or QOW) who has 1 related SAE; 1 related AE graded severe; 2 related AEs occurring on separate occasions, both graded moderate; or 3 consecutive doses judged “not tolerated” will be considered a treatment failure in the statistical analysis of each cohort and discontinued from ARC004 for safety reasons. Such subjects may be eligible to enroll in ARC008 on a QD regimen. If a site has not yet received approval for enrollment of subjects into ARC008, the subject will begin daily dosing and have visits in the Repeat Up-dosing period in ARC004. Once the subject reaches the target dose of 300 mg daily and maintains this dose for 2 weeks, that subject will be able to continue this dosing regimen and enroll in ARC008 when available.
 
Early discontinuations due to related AEs, and subjects unable to tolerate a prespecified amount (either ≥ 443 mg or ≥ 1043 mg of cumulative) peanut protein during the Exit DBPCFC, will be considered failures. If failures affect greater than 50% of any cohort, then prolongation of the dosing interval in any subsequent cohort will cease, and the remaining subjects will be administered AR101 300 mg at the longest dosing interval tolerated by a previous cohort (Section 7.8.3).
 
Early Discontinuations:
 
Subjects who are discontinued for an AE will have that AE evaluated from the onset until the event is resolved or medically stable, or for 30 days after the Early Discontinuation Visit, whichever comes first.
 
Subjects who are discontinued for reasons other than an AE and who do not enter ARC008 will be followed for safety for 30 days after the last dose of AR101, 2 weeks after the last food challenge, or until resolution or stabilization of all AEs ongoing at the time dosing is stopped, whichever is longer.
 
In addition, subjects who are discontinued from further AR101 dosing due to chronic or recurrent gastrointestinal (GI) AEs will be followed monthly for a minimum of 6 months, or until resolution or stabilization of all GI AEs.
 
For subjects who do not tolerate their nondaily dosing regimen and subjects who switch to daily dosing after missing their nondaily dose for > 3 days, the exit

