Throughout ARC004 EM, the first 2 doses at extended nondaily dosing intervals (BIW, QW, QOW) will always be administered under direct supervision in the clinic; QOD dosing is an exception and can be initiated at home. Thereafter, the doses will be administered at home as tolerated, and recorded in the subject diary. Investigators may, at their discretion, bring subjects back to the research unit for an observed dose at any time. All AR101 doses will be judged by the investigator to be tolerated or not tolerated according to criteria previously established in ARC003 and specified in [Section 6.5.2](#).

Dosing intervals should be as consistent as possible, preferably on the same days each week.

- In the BIW group, doses should be at least 3 days apart (eg. Monday and Thursday each week)
- In the QW group, doses should be taken on the same day (\pm 1 day) each week
- In the QOW group, doses should again be taken on the same day (\pm 2 days), every other week

Any subject receiving nondaily dosing (QOD, BIW, QW, or QOW) who has 1 related SAE; 1 related AE graded severe; 2 related AEs occurring on separate occasions, both graded moderate; or 3 consecutive doses judged “not tolerated,” will be considered a treatment failure in the statistical analysis of each cohort. These subjects will be returned to a 300-mg daily regimen by entering the Repeat Up-dosing period. For the majority of subjects, Repeat Up-dosing will be carried out in Treatment Pathway 2 of ARC008. However, if ARC008 is not available at the study site, subjects may start AR101 daily dosing and have visits in ARC004 until ARC008 is available, then continue dosing in ARC008.

No subject will be exposed to a longer dosing interval if evidence from previous cohorts suggests that doing so would more likely than not cause the subject to either experience more frequent or more severe AEs, or lose desensitization that he or she may have gained/maintained, compared to more frequent dosing. Because subjects in Cohorts 3B and 3C will have had 28 additional weeks of QD maintenance treatment, these subjects will be allowed to proceed to QOD and BIW dosing independent of Cohort 2’s experience according to the judgment of the Safety Monitoring Committee (SMC).

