Aimmune will monitor the safety and efficacy in each of the cohorts in accordance with internal procedures and escalate to the internal Safety Monitoring Committee (SMC) for review and recommendation for action. Only when sufficient efficacy and safety evidence is available on a cohort, will the SMC recommend that the next cohort advance to a longer interval between doses. Therefore, only after the safety and efficacy data from Group 2 cohorts are available, reviewed, and approved by the SMC, will the SMC allow the Group 1 patients to modify their once-daily regimen.

For more information on individual-, cohort-, and study-stopping rules, see [Section 7.8](#).

Down-dosing may be necessary during the Extended Maintenance Period due to safety or tolerability reasons; however subjects who had to be down-dosed remain in the Extended Maintenance Period during the dose adjustment. The duration of the Extended Maintenance Period does not reset if this occurs.

Early Discontinuations

Subjects who are discontinued and who do not enter ARC008 will be followed for safety for a minimum of 30 days after the last dose of AR101, 2 weeks after the last food challenge, or until resolution or stabilization of all AEs ongoing at the time dosing is stopped, whichever is longer. In addition, subjects who are discontinued from further AR101 dosing due to chronic or recurrent GI AEs will have experienced an AE of interest (AEI) and will be followed monthly for a minimum of 6 months, or until resolution or stabilization of all GI AEs ([Section 7.3.3.2](#) for more information about GI AEIs).

For subjects who do not tolerate their nondaily dosing regimen and subjects who switch to daily dosing after missing their nondaily dose for > 3 days, the exit DBPCFC will be omitted before discontinuation from ARC004 and enrollment in ARC008.

Subjects who are discontinued will not be replaced.

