4.3 Early Termination

4.3.1 Criteria for Early Termination

Any subject will be prematurely terminated from additional study drug treatment and excluded from any further study procedures (except for safety follow-up) for any one of the following reasons:

1. Life-threatening symptoms (Consortium of Food Allergy Research [CoFAR] Grade 4; refer to [Appendix 4](#)), including, but not limited to, anaphylaxis resulting in hypotension, neurological compromise, or mechanical ventilation secondary to peanut OIT dosing or any peanut food challenge
2. Severe allergic hypersensitivity symptoms (CoFAR Grade 3; refer to [Appendix 4](#)), including, but not limited to, those that require intensive therapy (to be determined by the investigator, but may include such interventions as intravenous (IV) epinephrine, intubation, or admission to an intensive care unit) or those that are recurrent. Subjects who experience severe symptoms (eg, severe nausea, rhinorrhea, or pruritus) that are not life-threatening, not requiring intensive therapy, and not associated with any other features indicating a serious clinical condition, and who the Investigator feels are suitable to continue with the study, will be discussed with the Medical Monitor and may continue the trial under close supervision, if both the Investigator and the Medical Monitor deem it appropriately safe to do so.
3. Pregnancy
4. Non-adherence (non-compliance) with study product dosing, as indicated by missing ≥ 7 consecutive dosing days on any 1 occasion, or 3 consecutive dosing days on 3 or more occasions during the Up-dosing Period, as this could constitute a potential safety issue (QD regimens only)
5. Medically indicated circumstances (eg, as part of the treatment for intercurrent AEs) that require missed study product dosing for >14 consecutive days, except for the voluntary 30-day hiatus for AEs occurring at or before the 20-mg dose (Group 1 only)
6. The subject elects to withdraw consent from all future study activities, including follow-up.
7. The subject is “lost to follow-up” (ie, no further follow-up is possible because attempts to reestablish contact with the subject have failed).
8. The subject’s continued participation in the study is assessed by the investigator to constitute a threat to the safety of the subject or the safe conduct of the study.
9. The subject dies (CoFAR Grade 5).

10. Poor control or persistent activation of secondary atopic disease (eg, atopic dermatitis, asthma)

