11. Started on angiotensin receptor blockers (ARBs), angiotensin-converting enzyme (ACE) inhibitors, beta-blockers, or other prohibited medications, with no alternative medications available per the prescribing doctor
12. The subject develops biopsy-documented eosinophilic esophagitis (EoE)

Subjects who discontinue study product prematurely due to AEs or other safety concerns should be encouraged to continue their participation in follow-up safety assessments. If a subject fails to return for scheduled visits, a documented effort must be made to determine the reason.

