7.8 Stopping Rules

7.8.1 Overall Stopping Rules

Considerations for early termination of a subject are listed in [Section 4.3.1](#). In addition, this protocol will institute the following stopping rules. The study will be suspended at any time that a treatment-associated death occurs in a subject receiving AR101 active therapy, or that the second of 2 subjects is admitted to the hospital, within 6 months of the first, as a direct consequence of dosing with AR101. Suspension of the study will entail halting the enrollment of subjects and refraining from any dose increases, but will not entail cessation of dosing unless so directed by the relevant competent authority and agreed to by the Sponsor.

The suspension will not be lifted and dose escalation will not be resumed until the information has been discussed with regulatory authorities and the regulatory authorities either concur with resumption of up-dosing or direct discontinuation of the study in their jurisdictions.

Aimmune Therapeutics, Inc. additionally reserves the right to discontinue the study at any time for any reason. The regulatory health authority(ies) and IRBs/ECs will be notified in the event of study discontinuation.

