7.8.2 Individual Stopping Rules

Individuals may stop the study at any time by withdrawing their consent if they experience subjectively intolerable AEs, dosing symptoms, or for any other reason. Because ARC004 is exploring alternative dosing schedules, the approach to individual stopping rules caused by dose-related AEs varies by regimen. All subjects discontinuing the study early and permanently discontinuing AR101 treatment will return to the CRC for an Early Discontinuation Visit no later than 14 days after the last AR101 exposure.

QD Dosing Regimens

When on QD dosing regimens (including Up-dosing and Maintenance for Group 1, and QD EM for both Groups, as applicable), 7 or more consecutive days of missed daily dosing due to non-compliance constitutes an individual stopping rule. During Up-dosing, Group 1 subjects must halt up-dosing and re-start with a reduced dose if more than 4 days of dosing are missed. Missing 3 or more consecutive days on 3 occasions while on daily dosing in any period is an individual stopping rule, as is missing 15 or more consecutive days of QD dosing for any reason.

QOD, BIW, QW, or QOW Regimens

Any subject receiving nondaily dosing (QOD, BIW, QW, or QOW) who has 1 related SAE; 1 related AE graded severe; 2 related AEs occurring on separate occasions, both graded moderate; or 3 consecutive doses judged “not tolerated” will be considered as a treatment failure and discontinued from ARC004 for safety reasons. Such subjects may be eligible to enroll in ARC008 and receive AR101 daily in the Repeat Up-dosing period. If ARC008 is not available, the subjects will begin daily dosing and have visits in the Repeat Up-dosing period in ARC004. Once the subject reaches the target dose of 300 mg daily and maintains that dose for 2 weeks, that subject will be able to continue this dose regimen until ARC008 is available.

Occurrence of any of the following will result in the cessation of dosing and the subject being discontinued from the study as an escalation failure nonresponder:

- Failure to accomplish up-dosing of study product after 3 attempts
- Failure to identify a tolerated dose of study product after 3 attempts at dose reduction

Finally, administration of 3 or more doses of epinephrine for the treatment of any dose-related allergic reaction in any subject during any period is an individual stopping rule.

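### Section 3.1.5 returns every nondaily treatment failure to daily AR101 and omits the events for which Section 4.3.1 stops AR101

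*Protocol*

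**What the plan says.** **The rule for nondaily failures.** The triggers are one related SAE, one related severe AE, two separate related moderate AEs, or three consecutive doses not tolerated. The consequence is worded differently from place to place.

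- Section 3.1.5: "These subjects will be returned to a 300-mg daily regimen by entering the Repeat Up-dosing period". The text then says that most subjects will do this in ARC008, and that where ARC008 is unavailable they *may* start daily dosing in ARC004. It later adds a pointer to Section 7.8: "For more information on individual-, cohort-, and study-stopping rules, see".
- Synopsis, Study Procedures: the subject leaves ARC004 for safety reasons and *may* be eligible for daily dosing in ARC008. At a site without ARC008 approval, "the subject will begin daily dosing and have visits in the Repeat Up-dosing period in ARC004".
- Section 7.8.2: again *may* be eligible, and where ARC008 is unavailable, "the subjects will begin daily dosing and have visits in the Repeat Up-dosing period in ARC004".
- Sections 3 and 6.5.7 are permissive throughout (an option, or *may*).

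**The rule for stopping AR101.** Section 4.3.1 opens "Any subject will be prematurely terminated from additional study drug treatment and excluded from any further study procedures (except for safety follow-up"). Three of its items matter here.

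- Item 1 covers CoFAR Grade 4 symptoms.
- Item 2 covers Grade 3 hypersensitivity symptoms, "including, but not limited to, those that require intensive therapy (to be determined by the investigator"), and recurrent ones. Milder severe cases may continue if the investigator and the Medical Monitor both agree.
- Item 12: "The subject develops biopsy-documented eosinophilic esophagitis (EoE").

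**The link between them.** Section 7.8.1 points to Section 4.3.1 and continues: "In addition, this protocol will institute the following stopping rules".

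**The concern.** A related life-threatening reaction to a nondaily dose is both a related SAE and a Grade 4 event. Section 3.1.5 then says the subject will return to daily AR101, and Section 4.3.1 says AR101 will end. Both are mandatory, and neither mentions the other.

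The cross-references do not settle it at the point of use. For severe symptoms Section 6.5.2 sends the investigator to Section 7.8.2, and Section 6.5.7 does the same for nondaily reactions. Section 7.8.2 does not mention Section 4.3.1; the link sits one subsection earlier, in 7.8.1. Section 3 also treats a less acute case more cautiously. A nondaily subject who tolerates less than 443 mg cumulative at the Exit DBPCFC may go back to daily dosing only on the investigator's judgment and after discussion with the medical monitor. The bullet for subjects who meet the Section 7.8.2 triggers has no such condition.

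What is at stake is redosing at 80, 120 or 160 mg of peanut protein after a reaction for which the protocol elsewhere stops treatment, in a population that includes children from age 4. The pathway is a real one: SAP Section 6.1 makes provision for Group 2 subjects who could not tolerate QOD or BIW and went back to QD.

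**Working it through.** The plan states no figure on this point, so the check is mainly of text.

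**Step 1. How binding is each version?**

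| Place | Main wording | Where ARC008 is unavailable | Refers to 4.3.1? |
|---|---|---|---|
| 3.1.5 | will | may | No |
| Synopsis, Study Procedures | may | will | No |
| 7.8.2 | may | will | No (7.8.1 does) |
| 6.5.7 | may | may | No |
| Section 3 | option | may | No |

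One place has an unconditional *will*. Two have it only in the fallback branch.

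**Step 2. Which events meet both rules, and what else stops AR101?**

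| Event on nondaily dosing | 4.3.1 | Other stops that reach the subject |
|---|---|---|
| Related Grade 4 reaction | Item 1 | 6.5.6 stop for stage 3 anaphylaxis, reached through 6.5.7; the 6.3.3.1 rule on stage 3 anaphylaxis or intensive therapy, carried into Repeat Up-dosing by 6.3.3.2; the 7.8.2 rule on 3 or more epinephrine doses |
| Grade 3 needing intensive therapy | Item 2 | 6.3.3.1 through 6.3.3.2; the epinephrine rule if met |
| Recurrent Grade 3, no intensive therapy | Item 2 | Epinephrine rule only, if met |
| Other Grade 3 | Item 2, unless investigator and Medical Monitor agree to continue | Epinephrine rule only, if met |
| Biopsy-documented EoE | Item 12 | 6.5.3.2 advises a low threshold for reducing or stopping with GI symptoms |

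EoE produces a conflict only if the subject also meets a nondaily failure trigger. Recurrent Grade 3 needs an earlier severe event, for example during daily dosing, because the first related severe AE on a nondaily regimen already ends that regimen. Section 4.3.1 item 8 (the investigator judges continued participation a safety threat) is available in every row.

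**Step 3. Scale.** The documents give no reaction rate for nondaily dosing, so only a rough range is possible.

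- Planned nondaily subjects (Protocol 7.8.3): 50 in Cohort 2 plus two thirds of 175 in Cohort 3 = 50 + 116.7 = 166.7, about 167. Group 1 is left out because SAP Section 2.3 keeps its QD subjects on QD.
- Lower rate: below 0.1% for life-threatening anaphylaxis (Protocol 1.4.1, stated for food challenges). Expected: below 0.001 × 166.7 = 0.17 subjects. Chance of at least one: below 1 − 0.999^167 = 0.154.
- Upper rate: below 1% for severe symptoms at some point in OIT dosing (Protocol 1.4.1). Expected: below 0.01 × 166.7 = 1.67 subjects. Chance of at least one: below 1 − 0.99^167 = 0.813.

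The upper rate counts any severe symptom over a whole course of OIT, and only some of those would meet item 1 or 2. Neither rate was stated for nondaily dosing, so these figures show an order of magnitude and are not estimates.

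**Step 4. Effect on the analysis.** The subject is a treatment failure under either instruction. SAP Section 6.1 puts safety data collected after the return to QD in listings and keeps them out of the summary tables.

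**The case against.** The best reply is that the protocol, read whole, already answers the question. Section 4.3.1 applies to any subject, and Section 7.8.1 makes the 7.8 rules additional to it. Section 6.5.7, which governs nondaily reactions, sends acute reactions to Section 6.5.6, where stage 3 anaphylaxis stops dosing at any time and more than two epinephrine doses for one reaction end it. Section 7.8.2 contains its own epinephrine stop. The mandatory wording in the Synopsis and 7.8.2 follows a sentence about subjects who *may* be eligible, so it can be read as saying where eligible subjects go.

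Most of this stands. It defeats two stronger readings that a reader might infer. The first is that all three rules order redosing of every subject with a related SAE; only Section 3.1.5 is unconditional. The second is that the protocol has no stop for life-threatening reactions on nondaily regimens; it has several.

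It does not remove the defect. Section 3.1.5 remains a mandatory instruction that contradicts Section 4.3.1, and the site has to infer which one governs. The overlapping stops also leave gaps: recurrent Grade 3 without intensive therapy and EoE depend almost wholly on Section 4.3.1. For other Grade 3 events item 2 requires two people to agree before treatment continues, and Section 3.1.5 requires neither.

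**Conclusion.** The point holds as a narrow wording conflict with a safety consequence. It should be corrected, because a rule that ends treatment should not depend on inference. It is unconditional in Section 3.1.5 and confined to sites without ARC008 in the Synopsis and Section 7.8.2. Few subjects are likely to be affected, the number cannot be estimated, and no endpoint, analysis or sample size changes.

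The conclusion assumes that Section 4.3.1 is meant to apply to nondaily subjects, which its wording and Section 7.8.1 support. It also assumes that a careful site would probably follow it.

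Two further inferences are not supported. Not every related severe AE creates a contradiction, because item 2 allows some subjects to continue. Nor can it be said that ARC008 would admit these subjects. The exclusion list in the ARC004 Synopsis and Section 3 omits the three items, but ARC008's own eligibility rules are not available to check.

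**What to change.** 1. In Section 3.1.5, change *will be returned* to *may be returned*. In the Synopsis and Section 7.8.2, change *will begin* to *may begin*.
2. In those three places and in Section 6.5.7, add:

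> unless Section 4.3.1 or 6.5.6 requires AR101 to be stopped, in which case AR101 is permanently discontinued; dosing gaps over 14 days on nondaily regimens are handled under Section 6.5.7

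The clause should refer to Section 4.3.1 as a whole. Naming only items 1, 2 and 12 would narrow item 2, whose examples are not exhaustive. It could also suggest that pregnancy, an investigator-judged threat, poorly controlled atopic disease or prohibited medication does not bar redosing. The last part is needed because item 5 ends treatment for medically required gaps over 14 days, and it is unclear how far its Group 1 limit reaches. Sections 3 and 6.5.7 offer daily dosing after such gaps.

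One detail to settle at the same time: Section 6.5.6 stops dosing at two or more epinephrine doses in Table 7 but at more than two in its text. The amendment should say which applies.

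Adding the same events to the ARC008 exclusion list in the Synopsis and Section 3 is optional and secondary.

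Cost: three one-word changes and one clause in four places. Data collection, analysis and sample size are unaffected.
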